## Study Synopsis:

Anhedonia and abnormalities in reward behavior are core features of overweight/obesity (OW), a highly prevalent condition within MDD populations and is independently associated with reward disturbances. We therefore aimed to investigate the brain substrates subserving reward and motivation in adults with overweight/obesity. Herein, we are primarily interested in three overlapping, yet distinct aspects, of anhedonia. We are primarily interested in motivation, reward valuation, and reward learning towards addressing the measurement of each of these respective subdomains, eligible participants will complete validated gold standard measures (i.e. the Effort Expenditure for Rewards Task (EEfRT) (reward valuation), Probabilistic Reward Task (PRT) (reward learning), and the Monetary Incentive Delay (MID) task (reward anticipation)).

Twenty adults with overweight/obesity will complete all tasks at a single visit with two of the tasks being completed prior to MRI and one of the tasks (i.e. EEfRT) will be completed during MRI acquisition.

The **primary aim** of this pilot study is to determine whether associations exist between obesity and decreased performance on the respective motivation/reward paradigms. In addition, associations between performance on reward tasks and functional connectivity, as measured by MRI and DTI, a secondary objective is to ascertain whether associations exist between performance on the motivation reward tasks and gold standard measures of food intake (i.e. food diary) and energy expenditure (i.e. calorimetry).

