## Methodology

### Participants

Participants will be identified at the Brain and Cognition Discovery Foundation (BCDF). Twenty subjects with obesity, will be enrolled. All patients will be assessed for concurrent psychiatric disorders (e.g. mood disorders). Eligibility criteria are as follows: inclusion criteria: (a) 18-65 years of age; (b) meeting DSM-V criteria for: (i) major depressive disorder (symptomatic or asymptomatic in any phase of the illness) or (ii) bipolar disorder I/II (symptomatic or asymptomatic in any phase of the illness); (c) ability to provide written and informed consent; (d) obesity 30 kg/m^2; (e ) weight under 440lbs; (f) shoulder-to-shoulder width under 60 cm; Exclusion criteria are as follows: (a) age below 18 or above 65; (b) use of benzodiazepines or consumption of alcohol within 12 hours of assessments; (c) abuse of marijuana; (d) physical,

cognitive, or language impairments sufficient to adversely affect data derived from assessments; (e) diagnosed reading disability or dyslexia; (f) clinically significant learning disorder by history; (g) history of moderate or severe traumatic brain injury; (h) other neurological disorders, or unstable systemic medical diseases; and (i) pregnancy and post-partum period (j) presence of any contra-indications for MRI; (k) weight above 440lbs; (l) shoulder-to-shoulder width greater than 60 cm. All subjects will be consented prior to initiating the study; (m) >45 BMI; (n) suicidality as determined by clinical discretion.

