#### 2. Illness Measurements:

- a. Severity of depression will be assessed with the Quick Inventory of Depressive Symptomatology (QUIDS)
- b. Measurement of anhedonia composite (SHAPS)
- c. Self-rated cognitive measurement (PDQ-5) Perceived Deficit Questionnaire 5
- d. Objective cognitive measurement (TMTA/B)
- e. Digit Symbol Substitution Test (DSST)
- f. UCLA Loneliness Scale

- g. Food Diary
  - h. Calorimetry
  - i. Anxiety Measurement (Hamilton Anxiety Scale) (HAMD)
  - j. Age of onset
  - k. Number of episodes
  - l. Number of hospitalizations
  - m. Duration of current episode
  - n. Psychiatric comorbidity
  - o. Number of treatments
3. Medical Assessment:
- a. Weight
  - b. Height
  - c. Waist circumference
4. Laboratory Measures:
- a. Blood glucose
  - b. Cholesterol and fractionation (E.g. HDL, LDL and triglycerides)
  - c. Insulin levels
  - d. Interleukin 1, interleukin 6, interleukin 10, tumor necrosis factor alpha, c reactive peptide, adiponectin, leptin, ghrelin, DPP-IV
  - e. Oxidative stress markers (e.g. TBARS)
5. Effort Expenditure for Rewards Task (EEfRT)
6. Monetary Incentive Delay (MID) task
7. Probabilistic Reward Task (PRT)
8. MRI Scan

All assessments and scan will be done on the same day.

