### **Primary and Secondary Outcome Measures**

The **primary outcome measure** in this study will be the association between performance on the EEfRT, MID, and PRT. Anthropometric data will be obtained from all participants at the day of the EEfRT assessment. Body mass index (BMI) will be measured using the formula  $BMI = \text{weight (Kg)} / \text{height (meters)}^2$ . The **secondary outcome** will be the association between the EEfRT/ MID/PRT and function reciprocity of the reward circuit/cognitive control network as measured by MRI/DTI. All participants will also have whole blood samples collected after a 12 hour fast. Metabolic parameters will be measured immediately in a single laboratory with the same assay. Insulin resistance and beta-cell function (i.e. insulin secretion) in basal state will be calculated from fasting plasma glucose and fasting insulin using the HOMA2 calculator (<http://www.dtu.ox.ac.uk>).

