### **Statistical Analysis**

Graph theoretical analysis (GTA) will be used to assess functional connectivity of the default mode network, cognitive control network, affect network and reward network. This is a

preliminary exploratory analysis, descriptive statistics will be conducted on the sociodemographic, clinical and metabolic parameters. Associations between obesity and alterations in functional connectivity will be the primary outcome of interest and additional coprimary outcome is the association between obesity and reward motivation as indexed by the EEfRT/MID/PRT task. Laboratory parameters will be used to explore potential mediational relationships between obesity and brain connectivity measurements, as well as reward performance.

For each variable, distribution normality will be assessed with one-sample Kolmogorov-Smirnov tests. Comparisons between groups will be conducted using independent samples t-tests and Mann-Whitney U (for normally and non-normally distributed variables, respectively). Participants are given 20 minutes to complete the EEfRT, and the number of trials completed during that time will vary among them (Table 1). Consistently with previous studies, only the first 50 trials will be used. Similar to previous studies using the EEfRT, we will use generalized estimating equation (GEE) models to test the effects of groups, reward magnitude and probability on the willingness to expend effort for rewards (i.e. percentage of trials on which the 'hard' task was selected). We will use an independent matrix, which best fit our data, and a binary logistic distribution to model the dichotomous outcome of choosing the hard versus the easy task. All GEE models will include reward magnitude, probability, and expected value (EV, defined as the interaction between reward probability and magnitude). In addition, each model will include a trial number as a covariate to control for possible effects of fatigue over the course of the task. Reward magnitude will be categorized in three groups: low (<\$2.30), medium (\$2.31-\$3.29), and high (>\$3.30). To assess associations between EEfRT and clinical and metabolic data, we will calculate the mean proportions of hard-task choices for all subjects.

Stepwise linear regression will then be used to identify significant predictors. MRI/DTI will be attained for all subjects.

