One of the key subcomponents of metabolic dysfunction in obesity is insulin resistance. Insulin resistance has been associated with depressive symptoms in epidemiological studies and, in clinical populations, with anhedonia specifically. Indeed, we observed a strong correlation between insulin resistance and willingness to expend effort in the MDD subgroup. Multiple brain regions that are relevant to reward systems have relatively increased expression of insulin receptors. Specifically, midbrain dopamine neurons, one of the main hubs of reward neurocircuitry, widely express insulin receptors. Imaging studies have reported that, in healthy individuals, insulin modulates brain activity in the hypothalamus, hippocampus and prefrontal cortex. A recent gene expression analysis reported that the differential expression of dopamine-related molecules in individuals with mood and psychotic disorders was related to altered expression of insulin signaling genes; an effect that was moderated by obesity in a region-specific manner (Mansur et al., 2018). As a result, peripheral insulin sensitivity has been shown to modulate reward behavior in humans. In obese adults, insulin resistance was associated with a stronger preference for immediately receiving a smaller, but certain, monetary reward over delaying the receipt of a larger, but less certain one (i.e. greater delay discounting).

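### Stepwise regression in 20 participants, from an unlisted pool and with no allowance for selection, gives p-values that do not hold at their nominal level

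*Combined protocol and SAP*

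**What the plan says.** Enrolment is fixed in the Participants section: "Twenty subjects with obesity, will be enrolled". The Statistical Analysis section introduces the EEfRT summary with "To assess associations between EEfRT and clinical and metabolic data, we will calculate the mean proportions of hard-task choices for all subjects" and then states: "Stepwise linear regression will then be used to identify significant predictors". Nothing more is said about this regression.

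The outcome is not named in the stepwise sentence; I infer it from the sentence before. The candidates are given as a class, not a list. No section gives the direction of stepping, an entry or removal level, a limit on model size, a multiplicity rule, shrinkage or validation.

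The measures that could enter are spread over two places. Measurements Obtained at Single Visit lists illness, anthropometric and laboratory items, including nine markers in one line: "Interleukin 1, interleukin 6, interleukin 10, tumor necrosis factor alpha, c reactive peptide, adiponectin, leptin, ghrelin, DPP-IV". Primary and Secondary Outcome Measures adds derived indices: "Insulin resistance and beta-cell function (i.e. insulin secretion) in basal state will be calculated from fasting plasma glucose and fasting insulin".

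Two statements bear on how much weight the result should carry. The synopsis calls this a pilot, and the Statistical Analysis section describes a "preliminary exploratory analysis, descriptive statistics will be conducted on the sociodemographic, clinical and metabolic parameters".

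**The concern.** Stepwise selection picks the terms that look strongest in these 20 people and then prints p-values as though those terms had been chosen beforehand. With no list and no entry level, a reader of the results could not tell how many measures were tried, so could not discount the p-values.

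The stake is a short list of predictors called significant, with no record of the search behind it. The Implications section makes this more than theoretical. It reports "Indeed, we observed a strong correlation between insulin resistance and willingness to expend effort in the MDD subgroup", without a size. A stepwise list from 20 participants could appear to confirm that finding, or put another marker in its place, and the printed p-values would not help to tell which.

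**Working it through.** The plan states no power, alpha or R-squared for this step, so there is no figure to reproduce. The check asks what the step would deliver.

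**Inputs.** From the plan: n = 20. Assumed, because the plan is silent: normal data; stepping in both directions; entry 0.05 with removal 0.10 as the conventional setting; 5, 10 or 33 candidates; common correlation between candidates from 0 to 0.5. There were 4,000 simulated studies per setting (Monte Carlo standard error at most 0.8 percentage points).

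**Size of the pool.** Five would be, for example, depression severity, anhedonia score, BMI, a HOMA2 index and one lipid. An upper reading of Measurements Obtained at Single Visit is 15 illness items + 3 anthropometric + glucose 1 + lipid fractions 3 + insulin 1 + 9 markers + TBARS 1 = 33. Adding BMI 1, total cholesterol 1 and HOMA2 indices 2 gives 37. The plan does not say that all of these are entered.

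**1. Chance of at least one false predictor, all candidates noise.** For independent candidates the check formula is 1 − (1 − entry level)^k. At 0.05 it gives 1 − 0.95^5 = 22.6%, 1 − 0.95^10 = 40.1% and 1 − 0.95^33 = 81.6%. At 0.01 with 5 candidates it gives 1 − 0.99^5 = 4.9%. Simulated results, from correlation 0.5 to correlation 0:

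| Candidates | Entry 0.01 | Entry 0.05 | Entry 0.10 |
|---|---|---|---|
| 5 | 4-5% | 20-24% | 34-41% |
| 10 | 8-10% | 29-40% | 49-65% |
| 33 (assumed upper reading) | 19-28% | 56-81% | 79-97% |

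These are family-wise chances. At entry 0.05 any one noise marker is selected only about 4-7% of the time.

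**2. Meaning of a printed p-value.** For the best of k independent noise candidates, a printed p of 0.01 corresponds to 1 − 0.99^k: 0.049 for k = 5 and 0.096 for k = 10. This does not depend on the entry level.

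**3. One real predictor, independent candidates, entry 0.05.** The Implications section gives no size, so true correlations of 0.3, 0.5 and 0.7 were tried. At least one false predictor is in the model in 18-21% of studies with 5 candidates and 37-39% with 10.

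**4. R-squared, if it is reported.** A baseline is needed first: one prespecified predictor, no search, kept only if p < 0.05. With no true effect p is uniform, so the median p among those kept is 0.025. On 18 degrees of freedom that is t = 2.445, and R-squared = t²/(t² + 18) = 5.98/23.98 = 0.25. Stepwise medians, given that something is selected:

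| Truth | True R-squared | One fixed predictor, kept if p < 0.05 | Stepwise, 5 candidates | Stepwise, 33 candidates |
|---|---|---|---|---|
| All noise | 0 | 0.25 | 0.26-0.27 | 0.48-0.54 |
| One real, r = 0.5 | 0.25 | 0.35 | 0.37 | 0.63 |

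At r = 0.7 (true R-squared 0.49) the stepwise median is 0.54 with 5 candidates and 0.58 with 10. With 5 candidates nearly all the inflation therefore comes from keeping only significant terms at n = 20, and the search adds about 0.02. The search adds materially only when the pool is large.

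**The case against.** The best defence is that this is a pilot labelled preliminary and exploratory, and that the step is not tied to the primary or co-primary associations. That stands as a limit on severity. It does not make a p-value computed after selection valid, and the stated purpose is to find significant predictors.

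A second point also stands: most of the false-positive chance is plain multiplicity. Unadjusted single correlations over the same pool would share it, so it should not be charged to the stepwise method alone.

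A third defence is that listing the candidates and levels would be enough, perhaps with a bootstrap check if R-squared is reported. That would fill the missing detail. The p-values printed for the selected model would still take no account of the search.

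Four stronger readings are tempting, and the documents do not support them:

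- That the chance of a false predictor is far above 5% whatever the settings. With 5 candidates and entry at 0.01 it is about 4-5%, and the plan fixes neither number.
- That more measures than participants will be entered, so that 56-81% is the expected rate. The plan names a class of data and nowhere says that every item goes in.
- That the plan will publish an inflated R-squared. It never mentions R-squared.
- That the stepwise search is the main source of R-squared inflation. In a short pool it is not, and with a strong real predictor the inflation is small.

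**Conclusion.** The point holds in a limited form. The absence of a candidate list, entry level and selection allowance is certain from the text, and so is the consequence that the selected model's p-values are not valid at face value. The size is conditional. At an assumed entry level of 0.05 with only noise, the chance of a false predictor is about one in five to one in four with 5 candidates, and 29-40% with 10. The higher figures need a pool that the plan does not commit to. If an R-squared is given, it will be too high, by an amount that depends on the pool and on how strong any real predictor is.

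This is worth correcting before the data are examined. It concerns only the stepwise step, and leaves the GEE models, the mediation analysis and the co-primary associations untouched.

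**What to change.** Replace the stepwise sentence with wording such as: *A short list of clinical and metabolic measures will be named before the data are examined. Each will be related to the proportion of hard-task choices by a Spearman correlation with its 95% confidence interval. All will be reported whether or not significant, the number of measures will be stated, and the results will be labelled hypothesis-generating.*

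If a multivariable model is wanted, for example to adjust for psychotropic medication (named as a possible confounder under Implications), it should contain at most two or three predictors fixed in advance, with no data-driven selection. The sponsor should choose them.

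If any result is to be called significant, adjust the p-values across the list, for example by Benjamini-Hochberg. For this exploratory step the adjustment is optional because it costs sensitivity. With 5 measures and one real predictor at r = 0.5, stepwise selects that predictor about 62% of the time and adjusted Spearman flags it about 33% of the time. That trade-off is the sponsor's to make.

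The remaining cost is wording and a little analysis work, with no new data. The intervals will be wide. For an observed Spearman correlation of 0.5, Fisher's z is 0.549 with standard error √(1.06/17) = 0.250, giving a 95% interval of about 0.06 to 0.78. That width shows what 20 participants can support.

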## **Data Handling**

### Personal Data Protection

All data collection material will be de-identified. Participant records will be distinguished using participant identification (PID) numbers.

### **Data Retention**

Records and documents pertaining to the conduct of the study as well as all data collected as part of the study will be retained in a secure place for 25 years in accordance with Health Canada regulations. All data collected throughout the study will be kept with membership of the BCDF for 25 years.

### **Participant Protection**

Participants will not be placed at any risk as a result of the study. Information obtained will be maintained in a secure and confidential fashion. No participant will be coerced and/or placed under duress to complete study procedures.

## **Implications**

We believe our results will comport with the notion that obesity is subserved by disturbances in reward circuits and cognitive control networks. We believe that alterations in reward and motivation are fundamental brain disturbances due to obesity. The Research Domain Criteria (RDoC) construct of reward is a core domain for the overlap between mood and metabolic disorders. We believe our results will show that obesity moderates and as a consequence of disturbance in reward and motivation and functional disconnectivity.

Mechanistically, a recent genetic study identified multiple genes that are shared between mood and metabolic disorders; and revealed an over-representation of genes involved in

dopamine signaling, which plays a crucial role in anhedonia and reward processing. In addition, obesity and MDD have a shared biosignature, with well-documented involvement of inflammatory mechanisms, hypothalamic–pituitary–adrenal (HPA) dysregulation, and oxidative/mitochondrial stress. Replicated neuroimaging studies have reported specific morphological alterations of the MDD and obesity comorbidity, implicating mainly medial prefrontal areas. Conversely, these areas are an important hub of reward valuation, and are known to be affected by, for example, inflammatory and metabolic mediators.

One of the key subcomponents of metabolic dysfunction in obesity is insulin resistance. Insulin resistance has been associated with depressive symptoms in epidemiological studies and, in clinical populations, with anhedonia specifically. Indeed, we observed a strong correlation between insulin resistance and willingness to expend effort in the MDD subgroup. Multiple brain regions that are relevant to reward systems have relatively increased expression of insulin receptors. Specifically, midbrain dopamine neurons, one of the main hubs of reward neurocircuitry, widely express insulin receptors. Imaging studies have reported that, in healthy individuals, insulin modulates brain activity in the hypothalamus, hippocampus and prefrontal cortex. A recent gene expression analysis reported that the differential expression of dopamine-related molecules in individuals with mood and psychotic disorders was related to altered expression of insulin signaling genes; an effect that was moderated by obesity in a region-specific manner (Mansur et al., 2018). As a result, peripheral insulin sensitivity has been shown to modulate reward behavior in humans. In obese adults, insulin resistance was associated with a stronger preference for immediately receiving a smaller, but certain, monetary reward over delaying the receipt of a larger, but less certain one (i.e. greater delay discounting).

In humans, insulin resistance is associated with less endogenous dopamine at D2/3 receptors in the ventral striatum and nucleus accumbens, in both obese and non-obese adults. Another study documented that weight loss following bariatric surgery was associated with an increase in D2 receptor availability. In effort-based decision-making, evidence indicates that dopamine responsivity, particularly in the striatum and ventromedial prefrontal cortex, is strongest for low probability trials. Conversely, we observed a stronger effect of overweight/obesity in the low reward trials. If overweight/obesity and the peripheral measures of insulin resistance used herein do indeed reflect and/or are associated with brain insulin resistance, it could be posited that disturbances in central insulin signaling lead to decreased dopamine sensitivity, resulting in an increased likelihood to choose low-effort options. This hypothesis, however, has two principle outstanding questions. First, it relies on the assumption that peripheral and brain insulin sensitivity are correlated (or that peripheral measures are reliable indicators of central processes), which is insufficiently characterized. Direct measurements of brain insulin sensitivity, and its relationship to dopamine signaling and effort-based decision-making, are necessary.

Second, it assumes that disturbances in insulin signaling are the principle mediators of the changes in dopamine function; an idea that does have support in the literature, but cannot be fully ascertained in a cross-sectional study. Moreover, recent evidence has indicated that the brain is also as an important regulator of systemic glucose and energy metabolism. For example, bromocriptine, a potent dopamine D2 receptor agonist, has been shown to improve glucose metabolism in humans. Dopamine release in the striatum might enhance whole-body insulin sensitivity, whereas inhibition of dopamine activity might reduce it. Therefore, individuals predisposed to lower central dopamine activity may be more susceptible to the development of obesity and insulin resistance states. Disturbances in reward behavior,

particularly effort, might also affect peripheral metabolism indirectly, through lower levels of physical activity and changes in dietary quality and/or patterns. In addition, other important factors might confound and/or mediate the association between obesity and effort in MDD, such as the use of psychotropic medications. There is a need for longitudinal studies, with carefully selected and described samples, to answer these questions.

There is, however, evidence indicating that circadian rhythms can affect reward behavior, dopamine signaling and glucose/insulin metabolism; and are as well a prominent component of the overlap between mood and metabolic disorders. The potential effects of circadian rhythms should be directly explored and/or accounted for in future work in the area.

In conclusion, we believe that obesity is a result of, and induces, disturbances in reward/motivation and cognitive control. There is a need to parse the substrates that subserve motivation/reward disturbance in adults with obesity. There is an additional need to evaluate the disturbance in reward/motivation with a rigorous paradigm i.e. EEfRT. The results of this proposal will also reinforce the brain and body consequences of obesity.

This study is supported by an unrestricted research grant from Bausch Health to the Brain and Cognition Discovery Foundation, Toronto, ON.

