## Procedures for Participants

### **Visit 1**

The single visit entails the provision of detailed study information to participant and obtainment of informed written consent, as well as completion of all questionnaires, activities, MRI, and participant compensation. The psychiatrists will assess participants' eligibility based on inclusion/exclusion criteria and confirm a diagnosis of MDD or BD based on their scheduled appointment visit. Demographics including date of birth, sex, and race will be recorded. Years of education will be recorded as well. Psychiatric and medical history, number of psychotropic medications received according to participant self-report/clinical chart review, as well as anthropometrics (including height, weight and waist circumference) will be measured. Participants will complete a series of questionnaires to assess their illness. These include: Quick Inventory of Depressive Symptomatology (QIDS), Snaith-Hamilton Pleasure Scale (SHAPS), Perceived Deficits Questionnaire for Depression (PDQ-5-D), Hamilton Depression Rating Scale (HAMD). Participants will also have loneliness assessed by participating in the UCLA Loneliness Scale. All self-reports will be administered by a member of the study team. Participants will record their food intake via a Food Diary, and will have a Calorimetry test taken. Participants will also complete cognitive measures including the Trail Making Test A/B (TMT A/B), and the Digit Symbol Substitution Test (DSST). Participants will then complete the Monetary Incentive Delay (MID) task, as well as the Probabilistic Reward Task (PRT). All study procedures will take place in a quiet setting. Fasting (12-hours) clinical and research bloodwork will also be collected. Participants will be escorted by a study member to the MRI facility where they will complete the MRI and the Effort Expenditure for Rewards Task (EEfRT). Upon completion of the MRI, participants will receive the reimbursement fee for their participation in the study.

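### HOMA2 is computed for every participant with no rule for insulin users, and no analysis is planned for participants whose BMI or insulin reflects surgery, weight-loss treatment or glucose-lowering drugs

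*Combined protocol and SAP*

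**What the plan says.** All references are to the combined protocol and SAP.

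- **Participants.** "Twenty subjects with obesity, will be enrolled". The weight criterion concerns present obesity ("d) obesity 30 kg/m" squared), with a ceiling at a BMI of 45. Exclusions (a) to (n) do not name bariatric surgery, weight-loss drugs or programmes, diabetes, insulin or other glucose-lowering drugs. The nearest item is "other neurological disorders, or unstable systemic medical diseases", which leaves stable treated disease eligible.
- **Primary and Secondary Outcome Measures.** "Anthropometric data will be obtained from all participants at the day of the EEfRT assessment", so BMI is a same-day value. Every participant gives fasting blood, and insulin resistance and beta-cell function (glossed there as insulin secretion) "will be calculated from fasting plasma glucose and fasting insulin using the HOMA2 calculator". No exception is given.
- **Visit 1.** A general psychiatric and medical history is taken, with the "number of psychotropic medications received according to participant self-report/clinical chart review". There is no named item for metabolic drugs, weight-loss treatment or surgery.
- **Statistical Analysis.** The association of obesity with reward motivation is co-primary, and laboratory values are explored as mediators. No adjustment, exclusion or sensitivity analysis for metabolic or weight treatment is specified.
- **Implications.** One cited study is reported as showing that "weight loss following bariatric surgery was associated with an increase in D2 receptor availability". A dopamine D2 agonist "has been shown to improve glucose metabolism in humans". Insulin resistance is put forward as a leading mechanism.

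**The concern.** Two measurements may mean something different in treated participants.

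The firmer problem is HOMA2. The plan reads fasting insulin as the participant's own output. In someone who injects insulin, the measured concentration can include the injected hormone, and both HOMA2 outputs are built from it. Followed as written, the plan would place values without their intended meaning into the mediation analyses, on the variable that its own discussion treats as a leading mechanism.

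The weaker problem is BMI. After surgery or during weight-loss treatment, same-day BMI may understate the obesity that the reward system was exposed to. Whether this distorts the BMI-reward association depends on whether reward function follows current or former BMI, which the documents do not settle.

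At stake is the reading of the associations: with 20 people, a few treated participants could mix the correlates of obesity with those of treating it.

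**Working it through.** The plan gives no sample-size, power or alpha figure, so there is nothing of its own to reproduce. From the documents: n = 20 and BMI 30 to 45. Everything else below is assumed for illustration: two-sided 5% test, true r = -0.60, BMI evenly spread over 30 to 45, and SD of 0.5 for log insulin resistance.

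**1. Sensitivity of 20 observations.** The critical |r| is t/sqrt(18 + t²), with t the 97.5% point on 18 df, giving 0.444. By Fisher's z, the r detectable with 80% power is tanh((1.960 + 0.842)/sqrt(17)) = 0.59. A true r of -0.60 is thus only just within reach.

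**2. Chance of enrolling a treated participant.** The documents give no prevalence. The chance of at least one in 20 is 1 - 0.95^20 = 64% at an assumed 5%, and 1 - 0.90^20 = 88% at an assumed 10%.

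**3. HOMA2.** Suppose injected insulin multiplies the measured value by f in k of 20 participants, independently of true resistance. The shift in SD units is d = ln(f)/0.5, which is 1.386 for f = 2 and 2.773 for f = 4. With p = k/20, r is multiplied by 1/sqrt(1 + p(1 - p)d²).

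| k | f | Factor | r by formula | Mean simulated r | Chance of significance |
|---|---|---|---|---|---|
| 0 | – | 1 | -0.60 | -0.59 | 0.84 |
| 1 | 2 | 0.957 | -0.57 | -0.56 | 0.79 |
| 1 | 4 | 0.856 | -0.51 | -0.50 | 0.67 |
| 2 | 2 | 0.923 | -0.55 | -0.54 | 0.75 |
| 2 | 4 | 0.769 | -0.46 | -0.44 | 0.54 |

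Simulated values (4,000 replicates per row) are slightly smaller in size than the formula's, partly because the mean sample r at n = 20 lies a little nearer zero than the true value.

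**4. BMI.** The SD of an even spread over 30 to 45 is 15/sqrt(12) = 4.33, so an assumed 10-unit loss is d = 10/4.33 = 2.31 SD, and d² = 5.33. Eligibility is on current BMI, so that SD already describes the observed values, treated people included. If reward function still reflects former BMI, the treated participants add variance to the outcome, and r is multiplied by 1/sqrt(1 + 0.36 × 5.33 × p(1 - p)), where 0.36 = 0.60².

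- Two treated, no recovery: 1/sqrt(1 + 0.36 × 5.33 × 0.09) = 0.923, so r = -0.55. Simulation also gives -0.55 against -0.60, about 8% attenuation; the chance of significance falls from 0.86 to 0.78.
- Reward function fully follows current BMI: no distortion (simulated r about -0.60 for any number treated).
- Placement matters too. If both treated participants are put at BMI 30 to 35 with no recovery, simulated r is -0.45 (40,000 replicates); with half recovery it is -0.54.

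The BMI result is therefore set by what is assumed.

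**The case against.** **The study is an exploratory pilot.** No confirmatory error rate is at risk, and the Implications section acknowledges both confounding in general terms and the limits of cross-sectional data. This stands and limits the harm to interpretation. It does not supply a rule for HOMA2.

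**The medical history could reveal surgery or insulin use.** This also stands. A reader might infer that psychotropic drugs are the only treatment captured; that is too strong. But no specific item ensures that metabolic treatment is recorded, and no planned analysis uses it.

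**The insulin assay is not described.** Correct: the documents do not say what it detects, so the claim is that measured insulin can include the injected hormone, not that every value is wrong.

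**The protocol does not say that treatment alters the reward system.** A reader might infer this from the Implications section. The text reports an association between surgical weight loss and receptor availability from one study; it concerns neither task performance, nor weight-loss drugs, nor insulin therapy. The dopamine agonist is cited on glucose regulation. The stronger reading is unsupported.

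**A fixed attenuation for BMI.** A reader might apply the measurement-error formula from step 3 with d = 2.31 and obtain factors of 0.89 and 0.82, that is 11% and 18% for one and two participants. That adds error to an SD that already describes observed BMI. It also assumes that reward function does not follow the weight loss, the opposite of a reward system changed by treatment.

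**Conclusion.** The point holds for HOMA2 and for the missing sensitivity analysis. Nothing in the plan prevents an insulin user from enrolling or from contributing a HOMA2 value that does not represent that person's own secretion or resistance. One or two such values among 20 can materially shift a correlation: from -0.60 to between -0.56 and -0.44, conditional on the assumed true r, log SD and 2- to 4-fold inflation. The need for a rule does not depend on those figures.

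For BMI, the conclusion is limited to uncertainty. The effect runs from none to about 8% for two participants with an assumed 10-unit loss and no recovery of reward function, and is larger only if those participants are also assumed to cluster at the bottom of the BMI range. A reader might infer that treated participants would dominate the result, or that they must be excluded. The documents support neither: they do not say how many would enrol, and restricting entry to a 20-person pilot is a trade-off for the sponsor and investigator.

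**What to change.** 1. In Primary and Secondary Outcome Measures, state that HOMA2 is not calculated for participants using insulin.
2. Within the medical history already taken at Visit 1, record use of insulin, other glucose-lowering drugs and dopaminergic drugs, current weight-loss treatment, and previous bariatric surgery.
3. In Statistical Analysis, add a sensitivity analysis that repeats the obesity-reward and HOMA2 associations without the treated participants, and report how many were removed.

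The cost is a few history items and two sentences of analysis text, with no new procedure. One or a few HOMA2 values will be missing. Removing treated participants may also narrow the range of insulin resistance, so the sensitivity analysis should be read beside the main one and not as a replacement. Whether eligibility should change is left to the sponsor and investigator.
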